14 STATISTICAL METHODS

14.1 ANALYSIS POPULATIONS

All enrolled subjects will be used to summarize subject disposition, demographic and baseline characteristics, medical history, and prior/concomitant medications.

The analysis population will use all available subject data to evaluate the effect of the Obagi 360 system for photodamage. No imputation of missing data will be performed.

The safety population includes all enrolled subjects who applied any amount of study product. This population will be used for product exposure and all safety analyses.

14.2 STATISTICAL ANALYSIS

14.2.1 SUBJECT ACCOUNTABILITY

Subject disposition and reasons for discontinuations will be summarized.

14.2.2 DEMOGRAPHICS AND BASELINE CHARACTERISTICS

Demographics and baseline characteristics will be summarized.

14.2.3 ANALYSIS OF IMPROVEMENT IN PHOTODAMAGE BY INVESTIGATOR

For each of the components of the Investigator's Skin Grading Assessment for improvement in photodamage, the data will be summarized in the format shown in Table 4.

In the case of the Investigator's Assessments asked at each timepoint, a Paired T-Test will be used to compare the individual scores at each time point relative to their respective baselines for each treatment cell. The net change scores for each attribute will be shown as a distribution and converted to the number of subjects who showed "improvement", "stayed the same" or "worsened".

For all analyses unless otherwise specified, a two tailed p < 0.05 will be taken as the level of significance.

Table 4 Format for Summary of Investigator's Skin Grading Scale

Investigator's Skin Grading Skin Grading Component (e.g., Sallowness)

	Mean ± S.D.	P-value					
Baseline							
Day 14							
Day 28							
Day 56							
Day 84							
Net Change from Baseline							

Day 14	
Day 28	
Day 56	
Day 84	

Distribution of (Net Change) Scores

	-4	-3	-2	-1	0	+1	+2	+3	+4
Day 14									
Day 28									
Day 56									
Day 84									
	Two		d				7	X/orac	^

	ımprovea	=	vvorse
Day 14			
Day 28			
Day 56			
Day 84			

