7.2 STUDY SUBJECT ASSIGNMENT, RANDOMIZATION, AND BLINDING

This study is being conducted open-label. There is no blinding of the investigator or subject. Enrolled subjects will be assigned a sequential number at each site.

Study center(s) will be instructed to enroll approximately 30% of subjects who are prone to mild breakout (non-inflammatory).

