8 SELECTION OF STUDY POPULATION

8.1 INCLUSION CRITERIA

Individuals eligible for inclusion in this study must meet all the following criteria:

- 1. Female subjects between the ages of 25-40
- 2. Fitzpatrick skin type I-IV
- 3. Investigator Assessment of Overall Integrated Facial Photodamage of mild to moderate (score of 2 5 inclusive; Section 11.1) and prone to breakouts (non-inflammatory), as assessed by the investigator.
- 4. Willing to withhold use of all other topical skincare products during the study with the exclusion of facial cleansers and Latisse. Make-up is allowed.
- 5. Willing to withhold all facial treatments during the course of the study including toxins, fillers, microdermabrasion, IPL, peels, facials, laser treatments, tightening treatments. Waxing and threading is allowed but not facial laser hair removal.
- 6. Willing to remove all makeup at every visit for pictures.
- 7. Willing to sign Photo release.
- 8. Willing and able to give written informed consent.
- 9. Subject is able to follow study instructions, accessible for treatment and follow-up at the specified time on the specific required study visit days, and likely to complete all study requirements
- 10. Female subjects of child bearing potential agree to take a urine pregnancy test at the Baseline visit, end of the study and when deemed appropriate by Investigator and/or Sponsor. Subjects of childbearing potential is defined as any female who has experienced menarche and who:
 - a. Has not undergone successful surgical sterilization (i.e. hysterectomy or bilateral oophorectomy)

Or

b. Is not post-menopausal (i.e. amenorrhea equal to or greater than 12 consecutive months)

Or

c. Is on hormone replacement treatment (HRT) with a documented serum follicle stimulating hormone (FSH) level of >35mIU/mL

- 11. Be using an acceptable method of contraception throughout the study if they are female of child-bearing potential. Acceptable methods of birth control include: oral and other systemic contraceptives, double barrier, bilateral tubal ligation, partner vasectomy and abstinence. Oral and other systemic contraceptives must be stable for three months prior to the Baseline visit. Patients on oral contraceptives agree not to alter their oral contraceptive, including dose or regimen for the duration of the study

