14.3 SAMPLE SIZE

Forty subjects will be enrolled. Forty subjects are adequate to obtain information on the antiaging effects of the Obagi 360 system.

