Appendix 3: Subject's Self-Assessment

(PART 2)

Questionnaire – Day 14, 28, 56 and 84/EOS

SI	JBJECT'S	SELF-A	SSESSMENT	QUESTIONNAIRE ((PART 2)
	JUJULU I		COLUCIAL	Q C E D I I C I II II II II I	TILLE W/

(THE SUBJECT SHOULD COMPLETE THIS QUESTIONNAIRE AND INITIAL THE BOTTOM OF THIS PAGE IN THEIR OWN HANDWRITING)

For each question, please put a check mark ($\sqrt{}$) in the column you agree with the most, use one check mark for each statement.

Please rate your agreement with the following statements:

	Strongly Agree	Agree	Indifferent	Disagree	Strongly Disagree
My skin clarity has improved					
My face feels rejuvenated					
My skin has a youthful glow/radiance					
My skin vitality has increased					
My skin looks and feels more hydrated					
My pores are less visible					
My breakouts are less visible					
My breakouts are less frequent					
My skin looks and feel smoother					

Would you recommend this product to a friend?	□Yes	□No
Would you want to purchase this product?	□Yes	□No
Would you continue using this product if made available?	□Yes	□No

Subject	in	initial.	

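### Inclusion criterion 3 and Section 7.2 conflict on who is breakout-prone; if Section 7.2 governs, the all-subject analysis of Breakouts is diluted and can mix opposite changes

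*Protocol*

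**What the plan says.** **Who is enrolled.** Protocol Section 8.1 introduces its list with "Individuals eligible for inclusion in this study must meet all the following criteria". Criterion 3 asks for an overall photodamage score of 2 to 5 "and prone to breakouts (non-inflammatory), as assessed by the investigator". The synopsis repeats the criterion. Section 7.2 says: "Study center(s) will be instructed to enroll approximately 30% of subjects who are prone to mild breakout (non-inflammatory"). Section 14.3 sets the size: "Forty subjects will be enrolled".

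**How Breakouts is measured.** Section 11.1 grades six components, Breakouts among them, on a static scale from 0 (none) to 6 (severe). The entry minimum of 2 applies to the overall score only, so a baseline Breakouts score of 0 is allowed.

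**How it is analysed.** Section 14.1: "The analysis population will use all available subject data to evaluate the effect of the Obagi 360 system for photodamage". Section 14.2.3 gives each component the same treatment: "a Paired T-Test will be used to compare the individual scores at each time point relative to their respective baselines for each treatment cell". Table 4 adds the distribution of change scores and the counts Improved, equal and Worse. Section 14.2.4 summarises each self-assessment question over the subjects who reply, by visit and without testing. Appendix 3 Part 2 has two breakout items, one on frequency and one reading "My breakouts are less visible". Both take one of five agreement levels, with no Not applicable box.

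**The concern.** Read literally, the two enrolment statements cannot both hold: either all 40 subjects are prone to breakouts or about 12 are. The choice decides what the Breakouts results mean.

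If the population is mixed, a subject with no breakouts at baseline cannot improve on this component. She can only stay equal or worsen, yet she counts fully in the mean change and in the denominator for Improved. The all-subject line then combines two questions: whether existing breakouts get better, and whether new ones appear in clear skin. These can move in opposite directions. In the questionnaire, subjects without breakouts are asked whether their breakouts have become less visible or less frequent, and their answers enter the reported percentages.

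This matters because the study has no control arm and its sample size rests on no stated effect. The mean change and the percentages are what will be read, and for the self-assessment they are the whole result.

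**Working it through.** The protocol gives no effect size, SD or power for Breakouts, so there is no figure of its own to reproduce. Inputs from the protocol are N = 40 (Section 14.3), a prone share f = 0.30 (Section 7.2) or 1.00 (Section 8.1, criterion 3), and a two-sided 5% level (Section 14.2.3). Everything else below is an assumption and is marked as such. No dropout is assumed.

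**1. Counts.** Section 7.2: 0.30 × 40 = 12 prone, 28 not prone. Criterion 3: 40 prone, 0 not prone.

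**2. Mean change.** If non-prone subjects do not change, the all-subject mean is f × δ, where δ is the mean change in prone subjects. With δ = −1.0 point this is 0.30 × (−1.0) = −0.30. Under criterion 3 it stays at −1.0.

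**3. Ceiling on Improved.** Let q be the share of non-prone subjects with a baseline Breakouts score of 1 or more (assumed), and let every prone subject be able to improve. The ceiling is f + (1 − f) × q:

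| q | Ceiling |
|---|---|
| 0 | 0.30 + 0.70 × 0 = 30% |
| 0.25 | 0.30 + 0.70 × 0.25 = 47.5% |
| 0.50 | 0.30 + 0.70 × 0.50 = 65% |
| 1 | 0.30 + 0.70 × 1 = 100% |

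**4. Constructed example.** Let the 12 prone subjects change by −1 (six), −2 (three) and 0 (three). Paired t-test on the changes:

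| Group | n | Mean | p | Improved / equal / Worse |
|---|---|---|---|---|
| Prone only | 12 | −1.00 | 0.0007 | 9 / 3 / 0 |
| All, the 28 others at 0 | 40 | −12/40 = −0.30 | 0.003 | 9 / 31 / 0 |
| The 28 others, six gaining one point | 28 | +6/28 = +0.21 | 0.011 | 0 / 22 / 6 |
| All, with those six at +1 | 40 | (−12 + 6)/40 = −0.15 | 0.23 | 9 / 25 / 6 |

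In the second row the percentage Improved falls from 9/12 = 75% to 9/40 = 22.5%, but the test remains clearly significant. In the last row, two groups that each differ from zero in opposite directions give a non-significant all-subject result.

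**5. Power.** Noncentral t for n = 12; simulation with 100,000 runs for the 12 + 28 mixture. The standardized change d in prone subjects is assumed.

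| d | 12 prone only | All 40, others fixed at 0 | All 40, others varying (SD half that of prone) |
|---|---|---|---|
| 0.5 | 35% | 34% | 23% |
| 0.8 | 71% | 69% | 47% |
| 1.0 | 88% | 87% | 65% |

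Pooling costs almost no power while the others stay at 0. It costs more once their scores vary.

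**6. Precision.** The 95% half-width in SD units is t/√n: 2.201/√12 = 0.64 for prone subjects only, 2.023/√40 = 0.32 for 40 subjects.

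**7. Questionnaire.** The size of the distortion cannot be computed. A non-prone subject may tick Indifferent, tick Agree or leave the item blank, and nothing in the protocol says which.

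**The case against.** The strongest reply is that criterion 3 is mandatory. On that text all 40 subjects are prone, and there are no unaffected subjects and no ceiling caused by them. That stands, and it is why the dilution is conditional. A reader might infer from Section 7.2 that the plan is for about 70% of subjects to be free of breakouts. The protocol as a whole does not support that: the 30% appears only there, and the wording might refer to mild breakout within a prone population. Against this, a 30% target for prone subjects has little purpose if all must be prone, so a mixed population remains a plausible intention.

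Second, being prone is a tendency, while the score is a grade on the day. Nothing in Section 11.1 equates not prone with 0. This also stands: the 30% ceiling is the worst case of a range.

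Third, a reader might infer that pooling destroys the test or conceals worsening altogether. Neither follows. The diluted example keeps p = 0.003, and Table 4 would show the 9 improved, 25 equal and 6 worse. It would not show which group each change came from.

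Fourth, the self-assessment denominator is subjects replying, Indifferent is available, and nothing is tested. True, but Indifferent does not identify a subject to whom the item does not apply.

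Finally, subgroup tables are often left to a SAP, which is not at hand here. That limits the weight of the reporting point. It does not resolve the enrolment conflict, and a later analysis plan cannot add an answer box to completed questionnaires.

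**Conclusion.** The point holds in conditional form, with medium confidence. What is certain is that Section 8.1 criterion 3 and Section 7.2 disagree as written on the share of breakout-prone subjects, and that the protocol sets one all-subject analysis for Breakouts and for the two breakout questions.

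The consequences depend on which passage governs. Under criterion 3, non-prone subjects cause no dilution. Under Section 7.2, the all-subject mean shrinks to about 30% of that in prone subjects (assuming the others do not change), and the ceiling on Improved lies anywhere from 30% to 100% depending on non-prone baseline scores. The significance test is little affected unless non-prone scores vary or worsen. In that case a benefit and a harm can offset each other, and the planned table cannot attribute them. The effect sizes, SDs, baseline shares and the six worsening subjects are illustrations, not protocol figures.

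**What to change.** 1. Reconcile criterion 3 (Section 8.1 and synopsis) with Section 7.2, so that the protocol states once whether all subjects or only a share are to be breakout-prone, and whether the 30% refers to proneness or to its severity.
2. Record prone status as a baseline data item. Table 1 and Section 13.1 do not list it at present.
3. If a mixed population is intended, report the Breakouts score (change and Improved, equal, Worse) and the two breakout questions by prone status beside the all-subject figures. Report new onset (0 to 1 or more) in non-prone subjects.
4. Add Not applicable to the two breakout questions in Appendix 3 Part 2, before the form is used.

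The cost is some wording, one baseline item and one answer option. The statistical cost is that the prone-subject estimate rests on about 12 subjects, with a 95% half-width of about 0.64 SD instead of 0.32 SD. Keeping the all-subject figure alongside preserves the planned summary.

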14.2.4 ANALYSIS OF SUBJECT'S SELF-ASSESSMENT

For the Subject's Self-Assessment, each question will be summarized separately using the proportion of subjects replying for each category (e.g., Strongly agree, Agree, Indifferent, Disagree, Strongly disagree) by visit. No statistical testing will be performed on the Subject's Self-Assessment.

14.2.5 ANALYSIS OF SAFETY

14.2.5.1 Analysis of Adverse Events

Safety analysis will include assessment (number and %) of all treatment-emergent AEs, any serious AEs, treatment-related AEs, and AEs leading to study discontinuation for each treatment group.

All AEs will be coded by the Medical Dictionary for Regulatory Activities (MedDRA).

Treatment-emergent adverse events (TEAEs) are defined as those AEs that either have an onset time on or after the start of study drug until the end of study.

Treatment-emergent AEs will be summarized for each treatment group by the overall incidence of at least one event, incidence by system organ class, and incidence by system organ class and CONFIDENTIAL AND PROPRIETARY INFORMATION OF OMP, INC.

preferred term. Each subject will be counted only once for each of the rates, regardless of the number of occurrences (events) the subject experiences. Treatment-emergent AEs will be summarized by severity and by relationship to study product.

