
Test product, dose and mode of administration:

Obagi 360 System consisting of: Obagi 0.5% retinol, Hydrafactor SPF30, and Exfoliating cleanser. The system will be used once daily for 3 months.

Reference therapy, dose and mode of administration:

None

Duration of treatment, enrollment and follow-up:

Duration of treatment period: 12 weeks

Criteria for evaluation:

- 1. Improvement in manifestations of photodamage assessed by the investigator using the Investigator's Skin Grading Assessment.
- 2. Assessment of improvement by the subject using the Subject's Self-Assessment.

Safety:

Safety variables include treatment-emergent adverse events (AEs), serious AEs (SAEs), treatment related AEs, and AEs leading to study discontinuation.

The investigator will assess the tolerability of the product at each visit.

Sample size:

Forty subjects will be enrolled. Forty (40) subjects are adequate to obtain information on the anti-aging effects of the Obagi 360 system.

Statistical methods:

The effect of the Obagi 360 system on photodamage will be evaluated using the Investigator's Skin Grading System. The changes from baseline in the scores will be summarized and tested for significance using the paired T-test for each time point. In addition, a summary of the distribution or scores (improvement or worsening) will be summarized and categorized as the number and proportion of subjects "Improved", "Equal to" or "Worse" than baseline.

For the Subject's Self-Assessment, the response to each question will be summarized by the proportion of subjects in each category. No statistical testing will be performed on the Subject's Self-Assessment.

Safety will be summarized by the incidence of adverse events over the study by body system and preferred term. The tolerability will be summarized by the proportion of subjects with none, mild, moderate, and severe for each assessment by visit.

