7 STUDY OBJECTIVE

To observe improvement in the appearance and the effects of the Obagi 360 skincare system when used consistently over a 3 month time period.

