8.5 STUDY SUBJECT WITHDRAWAL OR EARLY TERMINATION

8.5.1 WITHDRAWAL/EARLY TERMINATION

An early termination occurs when an enrolled subject ceases participation in the study, prior to completing the protocol. Subjects must be permitted to withdraw from the study at any time for any reason. Subjects may be withdrawn at any time at the discretion of the investigator or sponsor for safety, compliance, or other reasons. In general, subjects should not be withdrawn by investigators prior to completion of the study unless there is documentation of any of the following:

- The investigator believes that the subject has experienced significant or disabling treatment-related adverse events (AEs) that can be diminished or avoided by subject withdrawal. Discussion with Obagi prior to withdrawal is preferred.
- Subject withdrawal is in the best interest of the health of the subject. A withdrawal for medical reasons should document the specific condition for removing the subject.
 Discussion with Obagi prior to withdrawal is preferred.
- Lost to follow-up.
- Death.

The final safety evaluation required by the protocol will be performed at the time of the early termination, if possible. All subject withdrawals will be fully documented.

Subjects who discontinue prematurely from the study will not be replaced until approved by the sponsor.

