9.6 ASSESSMENT OF TREATMENT COMPLIANCE

The subjects will return to for follow up on Day 14, 28, 56, and 84 to ensure compliance to protocol procedures, including refraining from the use prohibited concomitant treatments or medications.

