12.1.4 PREGNANCY

All female subjects of childbearing potential must use an effective method of birth control during the course of the study, in a manner such that risk of contraceptive failure is minimized. Abstinence is allowed as a birth control method.

Before enrolling a female subject of childbearing potential in this clinical trial, the Investigator must review the following information about study participation:

- Informed consent/assent requirements
- Contraceptives in current use

Following review of this information and appropriate subject counseling, the Investigator or designee and the subject must sign the Informed Consent before study enrollment.

During the study, all female subjects of childbearing potential should be instructed to contact the Investigator immediately if they suspect they might be pregnant (e.g., missed or late menstrual period).

If a subject or Investigator suspects that the subject may be pregnant prior to study enrollment, the investigational product must be withheld until the results of laboratory pregnancy testing are available. If pregnancy is confirmed, the subject must not receive investigational product and must not be enrolled in the study. If pregnancy is suspected while the subject is receiving investigational product, the investigational product must immediately be withheld until the result of a urine pregnancy test is known. If pregnancy is confirmed, the study drug will be permanently discontinued and the subject will be followed until the pregnancy comes to term. A Pregnancy Report form will be submitted, initially and quarterly through the end of the pregnancy, which includes the outcome of the pregnancy and any complications occurring

during the pregnancy or the delivery. The timelines and sponsor contact(s) for submission of pregnancy related information will follow those of SAEs above.

An event that is serious must be recorded on the Adverse Events CRF and requires expeditious handling to comply with regulatory requirements. All initial SAEs and follow up reports that contain change in causality must be forwarded to Obagi within 1 business day upon receipt of SAE. In addition, the serious adverse event form and other SAE-related forms must be completed accordingly.

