14.2.5.2 Analysis of Tolerability

Tolerability will be assessed using the scale in Section 12.2. For each of the assessments, the proportion of subjects experiencing none, mild, moderate, and severe will be summarized by visit.

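### The safety summary counts adverse events that end study participation but not those that interrupt or end product use, and the by-visit tolerability table does not show who is off product

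*Protocol*

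**What the plan says.** Section 14.2.5.1 lists the planned adverse event summaries. The only one that concerns stopping is "AEs leading to study discontinuation for each treatment group". The synopsis has the same restriction: "treatment related AEs, and AEs leading to study discontinuation". Section 8.5.1 defines early termination by leaving the study: "An early termination occurs when an enrolled subject ceases participation in the study, prior to completing the protocol". It has no parallel definition for a subject who stops the product and stays.

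For tolerability, Section 12.2 has the investigator grade dryness/scaling, erythema, burning/stinging and itching from 0 to 3 at each visit. Section 14.2.5.2 then says that "the proportion of subjects experiencing none, mild, moderate, and severe will be summarized by visit". Neither section distinguishes visits on product from visits off product.

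Section 12.1 asks about adverse events since the last visit and records, for each event, severity, causality, action taken, resolution date and outcome. Section 9.2.2 has unused product returned at Days 28, 56 and 84. Section 13.2 completes the product accountability CRF at each visit, and Section 14.1 plans a product exposure analysis in the safety population, which takes in everyone who used the product at all. No step in Section 13.2 asks for the date of last application or for interruptions.

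**The concern.** Stopping a product and leaving a study are different events, and for an irritating topical the first may well happen without the second. If only the second is counted, the figure most readers will take as the rate of intolerance leading to stopping can only be too low. The by-visit table can err in the same direction. A grade taken after the product has been stopped, when the skin has settled, is tabulated alongside grades from subjects still applying it. The four graded signs are the local reactions most likely to make someone stop, so the gap bears on a main safety output of this uncontrolled study.

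This is not only a matter for an analysis plan. The protocol itself names the measure, and what the visits record is a protocol matter. A later plan could tabulate action taken, but it could not fully recover a stop date that was never collected.

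**Working it through.** The plan gives no figure to reproduce, so the check is a reading of the text followed by an illustration.

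**Following one subject.** Suppose she stops the creams on Day 20 because of burning, the burning settles before Day 28, and she attends Days 28, 56 and 84.

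1. *Safety population (14.1):* included, because she used the product.
2. *AEs leading to discontinuation (14.2.5.1, synopsis):* not counted, because she has not left the study as Section 8.5.1 defines it.
3. *Tolerability (12.2, 14.2.5.2):* Day 14 keeps whatever grade it was given. Days 28, 56 and 84 can each be graded none, with nothing to show that she was off product.
4. *TEAE tables (12.1, 14.2.5.1):* if she reports the burning at Day 28, it appears by severity and by relationship.
5. *Data on the stop (9.2.2, 12.1, 13.2):* action taken is recorded for the event and leftover product is returned, but no listed summary uses either to count product stops. Leftover amounts collected at Days 28, 56 and 84 do not reliably date a stop.

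**Size of the undercount.** Let *s* subjects leave the study for an AE and *k* others interrupt or stop the product for an AE but stay. N = 40 (Section 14.3).

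- Reported: s/40
- Including product stops: (s + k)/40
- Difference: k/40, so each such subject is 1/40 = 2.5 percentage points

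The difference is never negative, whatever *s* is.

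**Illustration for the tolerability table.** Assumptions: s = 0; all *k* subjects are graded none at Day 84; 8 other subjects have irritation at Day 84. The table as planned shows (40 − 8)/40 = 80.0% with none, whatever *k* is. Among subjects still on product the proportion is (40 − k − 8)/(40 − k). If the *k* subjects are not counted as none, it is (40 − k − 8)/40.

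| k | AE study discontinuations as reported | AE product stops, k/40 | None, as planned | None, on product only | None, stoppers not counted as none |
|---|---|---|---|---|---|
| 1 | 0% | 2.5% | 80.0% | 31/39 = 79.5% | 31/40 = 77.5% |
| 2 | 0% | 5.0% | 80.0% | 30/38 = 78.9% | 30/40 = 75.0% |
| 4 | 0% | 10.0% | 80.0% | 28/36 = 77.8% | 28/40 = 70.0% |
| 6 | 0% | 15.0% | 80.0% | 26/34 = 76.5% | 26/40 = 65.0% |

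The last column is an extreme: it treats every stopper as if she would still have had irritation at Day 84. Against subjects still on product, the planned table differs by only 0.5 to 3.5 points over this range.

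**The case against.** The strongest reply is that the irritation is not hidden. Subjects are asked about events since the last visit, and reported burning appears as a treatment-emergent event by severity and relationship. This stands. A reader might infer that stopping turns irritation into evidence of good tolerability across the whole safety report; that is true at most of the by-visit table and the discontinuation count.

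Second, Section 8.5.1 allows withdrawal for marked treatment-related events, and at the investigator's or sponsor's discretion more generally, so a subject with a severe reaction may well leave and be counted. This also stands, and it limits the gap mainly to milder irritation.

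Third, product return, accountability, a compliance review in Table 1 and an exposure analysis are all planned. It would be unfair to say that compliance is judged by attendance alone, although Section 9.6 ("The subjects will return to for follow up on Day 14, 28, 56, and 84 to ensure compliance to protocol procedures") names no measure of product use. These provisions help to identify stoppers, but they neither date the stop nor feed a stated summary.

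Two further inferences are tempting and not supported:

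- *Pregnancy.* Section 12.1.4 says: "If pregnancy is confirmed, the study drug will be permanently discontinued and the subject will be followed until the pregnancy comes to term". This does separate stopping product from follow-up, so the protocol is not wholly silent on the distinction. But it has nothing to do with irritation, and it does not say that skin or tolerability grading continues.
- *Efficacy.* Section 14.1 uses all available data, while the objective in Section 7 concerns the system "when used consistently over a 3 month time period". Including off-product grades is a defensible choice; if the effect fades off product, it dilutes a benefit and does not flatter one. A Day 84 result restricted to subjects still applying product would select those who tolerate it, so it is not an evident improvement.

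**Conclusion.** The point holds in a limited form. The stated discontinuation measure omits subjects who interrupt or stop the product because of an adverse event and remain in follow-up, and the by-visit tolerability table can record them as free of irritation without showing that they are off product. As a count of product stops due to AEs, the measure can only be too low.

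The size is unknown. The documents give no rate of product stopping, and every *k* above is an assumption. So are the 8 other subjects with irritation and the premise that nobody leaves the study for an AE. The one firm figure is 2.5 percentage points per subject with 40 enrolled. This is a modest reporting gap, worth closing because closing it is cheap.

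**What to change.** 1. In Section 14.2.5.1 and the synopsis, add a summary of AEs leading to interruption or permanent stopping of product, next to AEs leading to study discontinuation. Take it from the action-taken item that Section 12.1 already requires, coded so that interruption and permanent stopping can be tabulated.
2. On the existing product accountability CRF (Section 13.2), record any interruption since the last visit and the date of last application.
3. In Section 14.2.5.2, mark off-product visits in the by-visit table, for example by giving the number off product within each grade.

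A worst-grade-over-the-study table is not a substitute. In the Day 20 example the burning falls between two visits, so the worst recorded grade could still be none.

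The cost is one or two CRF fields, one summary line and a marker in an existing table, with no added visit. The tolerability report may look slightly less favourable. The change concerns recording and reporting only and proposes no clinical rule for stopping the product.
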